#### **AE Management**

If we found someone with a low attitude towards vaccines, we do not believe that it would be appropriate to try to change their attitude, since (1) further interaction with someone who had a negative experience with us is unlikely to make their experience more positive, and (2) we do not know for sure if this attitude was related to their participation in this study. However, we can provide materials from a neutral party (like pamphlets on HPV from the National CDC) to the study site locations, so that individuals can have a different perspective on the medical issue.

Of course, if a participant participates some physical adverse event, we are unsure how it could be linked to our study, but all study procedures will occur at an immunization clinic (which are co-located with larger medical facilities), and so the individual should be able to receive timely and appropriate care.

### **6.3 Data analysis and management**

#### **Data analysis plans**

As data are being collected and entered into a database, we will tabulate our endpoint – vaccine acceptability, which we will dichotomize from a Likert scale – on a weekly basis. And if these numbers fall below a certain threshold, we will follow the procedures as outlined in the “Expected AEs” section above.

#### **Reporting of AEs**

All physical AEs will be reported according to the two IRBs’ AE reporting guidelines. In addition, aggregate statistics about behavioral/attitudinal AEs will be reported if they cross the threshold listed in this document.

#### **Plan for data management**

Compliance of regulatory documents and study data accuracy and completeness will be maintained through an internal study team quality assurance process.

Confidentiality throughout the trial is maintained by keeping informed consent forms and questionnaires in separate locations, and destroying the questionnaires after they have been input into an electronic database. Informed consent forms will be kept for a period of time designated by the IRBs. The informed consent forms and questionnaires will be in a locked locker, in a locked room, at the Shanghai CDC, which is a complex of buildings with guards at each entrance.

The data will initially be stored in a secure online platform – such as Box – which is HIPAA compliant and which the University of Michigan supports. While the data are being collected, and while some personally identifiable information may be present in the database, this folder will be password-locked and only available to study team members.

We will also keep a record linking the participants’ ID number to their vaccination record number. This linkage file will be kept separate from the questionnaires, and it will be on the hard drive of a computer at the Shanghai CDC. The computer will be password-locked and will only be accessible to study team members.

#### **Data sharing**

---

Reproducibility and replicability of studies are both extremely important. Therefore, we plan to upload a final dataset (along with code detailing my statistical analysis) to a public repository, such as figshare.com. This dataset will have personally identifiable information removed – and the clinic location will be coded by a number (not the name of the location) to prevent individuals being able to locate members of the study and identify them.

## 7 Statistical Considerations

### 7.1 Study Outcome Measures

At the end of the survey, parents will respond to the statement, “I am willing to vaccinate my child against HPV,” using a five-point Likert scale from “strongly willing” to “not at all willing”. In the analysis, this outcome can be analyzed either as a continuous/ordinal outcome or as a dichotomized outcome (agree vs disagree).

### 7.2 Sample Size Considerations

Based on previous results, we are powering to detect a difference between 70% and 80% in the outcome between the two groups (see explanation below). This would require a simple random sample of 588 or an effective sample size of 994 based on a design effect of 1.69. The enrollment of parents will be in immunization clinics.

This sample size of providers is limited by the number of clinics (n=40), but because we are sampling few providers from each clinic, the design effect is negligible, and we should be able to provide an estimate of risk perception with a confidence interval of 8 percentage points (assuming an outcome proportion of 80%). The outcome is the proportion of individuals who respond “somewhat important” or “very important” to questions on a 5-point Likert scale.

### 7.3 Participant Enrollment and Follow-Up

I estimate the follow-up rate to be 80%, given figures in recently published studies from China: 86.1% (Lau, Gross, Wu, Cheng, & Lau, 2017), 83% (Choi, Steward, Miège, Hudes, & Gregorich, 2016), 80.3% (Xu, Byles, Shi, McElduff, & Hall, 2016), 79.8% (Guo et al., 2017).

Participants from previous waves will be contacted by phone and asked to come to the immunization clinic for an additional survey. The person contacting past participants by phone would be me, a master’s student, or staff from the vaccination clinic.

### 7.4 Analysis Plan

We will use standard regression methods to compare this outcome between the main study arms. To account for the complex survey design, all models will use survey procedures, including weights, clustering, and Taylor series estimation of variance.

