## 4 Study Design

Participants will be randomized into two groups to receive information about the HPV vaccine. This information will be depicted on a sheet of paper using graphs and words. For one group, they will receive information similar to how it was historically presented in the US (as a sexually transmitted disease). The other group will receive modified messaging that downplays both the “gendered” nature of the disease and the role of sexual transmission and emphasizes that HPV is a cancer. The exact messaging will be developed in consultation with a mentor, [name], and after taking related coursework (as part of training goal 1). Although I believe this latter method will result in higher acceptance of HPV, the former method of presenting the information is still ethical because it will replicate materials from the WHO (World Health Organization, 2014). We will also collect demographic and socioeconomic data, along with measures of exposure to various information sources, including traditional media, social media, and messaging from hospitals and doctors.

Parents will provide information at three different stages. For wave 1 (this protocol), they will spend 30 minutes at a clinic filling out a paper questionnaire. For wave 2 (a separate protocol to be developed in the future), they will be re-contacted by phone and asked if they want to come to the clinic again to participate in another study. The third stage of data collection involves us linking their questionnaire data to their child’s vaccination records; we notify them about this in the informed consent document, but since we will also collect their child’s vaccination record number at the time of wave 1, we will not need to recontact them in the future in order to access the electronic immunization registry.

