### 5.2 Inclusion and Exclusion Criteria

Participants can be included if they are parents of children 2-18 years old.

All vaccination providers at a clinic which offers an HPV vaccine are eligible.

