### 6.2 Expected Adverse Events

#### **Expected AEs**

Because we are not testing any therapy, are not taking any biological samples, and are only engaging in an educational/behavioral intervention, we do not expect any “physical” AE to occur. However, we potentially could change someone’s attitude about the HPV vaccine for the worse. Because our goal in this study is to identify ways in which we can improve acceptance of HPV vaccination, if it turns out that we are in fact making people more vaccine hesitant, that would be a behavioral/attitudinal AE.

Although no previous study in China has replicated exactly what we will plan to do, observational studies have found a variation in acceptability of HPV vaccine. One study in Hong Kong found “the prevalence of parental acceptability of HPV vaccination for the index son and daughter were: [...] 51.6% and 63.0% (free vaccination)” (Wang et al., 2018). Another study from Jinan found that “female students were more willing to take the HPV vaccine than male students (76.7% vs 58.6%)” (Xue et al., 2017).

If, from preliminary analyses (see below), we find that acceptability of the vaccine is less than 40% (about 10% to 20% less than acceptability of what was found in previous studies – we are using a lower number to account for variability in the study population characteristics), we will stop data collection (enrollment of new participants), notify the IRBs, and identify ways to change the protocol prior to re-starting data collection.

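### Section 7.4 gives child's sex no role, so the plan forgoes a small precision gain and cannot show whether the framing effect differs between parents of sons and parents of daughters

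*Combined protocol and SAP*

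**What the plan says.** Section 7.4 is the whole analysis plan, in two sentences. The first reads "We will use standard regression methods to compare this outcome between the main study arms". The second adds that "all models will use survey procedures, including weights, clustering, and Taylor series estimation of variance". No covariate, stratification factor, subgroup or interaction is named.

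Child's sex also has no role elsewhere in the design. Eligibility (section 5.2) is open to parents of sons and daughters alike: "Participants can be included if they are parents of children 2-18 years old". Section 4 describes randomization into two groups without mentioning stratification. The outcome in section 7.1 asks about the respondent's child, without saying which child is meant when there are several. Section 4 promises "We will also collect demographic and socioeconomic data", but does not list child's sex among the items or give these data a place in the model.

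Two other places make sex relevant:

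- **Section 4.** One arm receives "modified messaging that downplays both the “gendered” nature of the disease and the role of sexual transmission", together with an emphasis on cancer.
- **Section 6.2 (Expected AEs).** A Hong Kong study is quoted: "the prevalence of parental acceptability of HPV vaccination for the index son and daughter were: [...] 51.6% and 63.0% (free vaccination". A Jinan study is quoted as finding that "female students were more willing to take the HPV vaccine than male students (76.7% vs 58.6". The protocol uses these figures only to set its 40% stopping threshold.

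**The concern.** By the protocol's own citations, child's sex is associated with willingness, and one of the two messages is written partly to weaken the link between HPV and gender. It is plausible that such a message moves parents of sons and parents of daughters by different amounts.

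Two things follow. First, a baseline variable that predicts the outcome is left out of the comparison, which costs some precision and leaves chance imbalance uncorrected. Second, a single pooled contrast cannot tell a similar effect in both groups from an effect confined to one. If the arm-by-sex estimate is not stated in advance, any sex-specific result will be post hoc. That is foreseeable here, because section 6.3 plans to deposit the dataset publicly.

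Section 6.3 also has the paper questionnaires destroyed after data entry, so child's sex needs to be an item, and entered, from the start of wave 1.

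**Working it through.** **Inputs from the documents.** 70% v 80%, 588, design effect 1.69 and 994 (section 7.2); 1,000 parents (Protocol Summary); acceptability by sex (section 6.2).

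**Assumptions, because the documents do not state them.** Two-sided alpha 0.05, 80% power, 1:1 allocation, half sons and half daughters.

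**1. The plan's own figure.** Two proportions, pooled variance under the null, no continuity correction:

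n per arm = [1.960 × √(2 × 0.75 × 0.25) + 0.842 × √(0.70 × 0.30 + 0.80 × 0.20)]² / 0.10² = (1.200 + 0.512)² / 0.01 ≈ 293.2, rounded up to 294.

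The total is 588, and 588 × 1.69 = 993.7, or 994. Both stated figures reproduce.

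**2. Gaps by sex.** Parents: 63.0 − 51.6 = 11.4 points. Students' own willingness: 76.7 − 58.6 = 18.1 points. Only the first is the kind of outcome this trial measures, so results based on 18.1 are an upper case.

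**3. Variance explained by sex.** With a 50:50 split, R² = (gap/2)² / [m(1 − m)], where m is the overall proportion.

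| Gap | m from the cited study | R² | R² at m = 0.75 (plan's rates) |
|---|---|---|---|
| 0.114 | 0.573 | 1.3% | 1.7% |
| 0.181 | 0.6765 | 3.7% | 4.4% |

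**4. Effect on power.** 1,000 / 1.69 = 591.7, or 295.9 per arm, which gives 80.4% power for 70% v 80%. Dividing the per-arm number by (1 − R²), with R² of 1.7% and 4.4%, gives 81.0% and 82.1%. The gain is about 1 to 2 points of power.

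**5. Chance imbalance.** SD of the between-arm difference in the share of daughters = √(0.25 × 2/500) = 0.0316. At 1.96 SD the shift in the unadjusted arm difference is 1.96 × 0.0316 × 0.114 = 0.7 points, or 1.1 points with 0.181, against a 10-point target.

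**6. Arm-by-sex interaction.** Four cells of 250. The variance of the difference between the two arm effects is 2 × (0.21 + 0.16)/250 = 0.00296, so SE = 0.0544. With design effect 1.69 the SE is multiplied by √1.69 = 1.3, giving 0.0707. The documents do not say what design effect applies to this contrast, so both ends are shown.

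| Quantity | Design effect 1.0 | Design effect 1.69 |
|---|---|---|
| Interaction detectable with 80% power (2.80 × SE) | 15.2 points | 19.8 points |
| Power for a 10-point interaction | 45% | 29% |
| 95% CI half-width, interaction (1.96 × SE) | 10.7 points | 13.9 points |
| Power for 70% v 80% within one sex | 73% | 51% |

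**The case against.** The case against making much of this is strong, and most of it stands.

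- **The plan does not exclude sex.** Standard regression allows covariates, and demographic data will be collected. A reader might infer that sex has been ruled out; the documents show only that it is not pre-specified.
- **The primary estimate is not biased.** Randomization protects the unadjusted contrast. A reader might infer that the main result would be confounded by sex; it would not be.
- **No stated objective is left unanswered.** The primary objective asks how framing affects willingness, not whether the effect differs by child's sex. That the effect should differ is a reasonable hypothesis, but the documents do not state it.
- **Sex cannot be ranked as the strongest predictor.** Section 6.2 quantifies no other predictor, and the larger gap comes from students, not parents.
- **An interaction would not isolate the gender wording.** The modified message changes three things together: gender, sexual transmission and cancer. Parents of sons and of daughters could react differently to any of them.
- **Adjustment is not free on every scale.** The plan allows a dichotomized outcome. In a logistic model, adding a prognostic covariate changes the odds ratio being estimated, and the linear variance argument in the working does not carry over directly.

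What these points leave untouched is that the change is nearly free, brings a small gain in precision, and provides an estimate of possible effect modification that a pooled contrast cannot give.

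**Conclusion.** The point holds as a modest, low-cost improvement to section 7.4; it does not show a flaw in the primary comparison. The plan forgoes about 1 to 2 points of power (R² about 1-4%). It also leaves uncorrected a chance shift of 0.7 to 1.1 points at 1.96 SD of imbalance.

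The more substantive gap is the absence of any pre-specified estimate by child's sex, given a message written partly around gender. That estimate will be imprecise: 80% power only for a difference in arm effects of about 15 points, or 20 with design effect 1.69. Either figure exceeds the whole planned main effect of 10 points, so the result belongs in the report as an estimate with its interval, and a non-significant interaction would not show that the effects are equal.

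These sizes rest on the plan's 70% and 80%, 1,000 parents, and the assumed 50:50 sex split, 1:1 arms and two-sided alpha 0.05. An uneven sex split would make the interaction less precise still.

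**What to change.** 1. **Index child.** Define one per parent. The child whose vaccination record number is collected at wave 1 (section 4) is a natural choice, since the uptake outcome will be linked through that number. Word the willingness item to refer to that child.
2. **Questionnaire.** Record the index child's sex at wave 1 if it is not already an item. The documents do not say whether the linked record holds sex, so the questionnaire is the safer source.
3. **Section 7.4, primary model.** Name child's sex as a covariate. Report the arm effect as a risk difference for the dichotomized outcome, or a mean difference for the 5-point scale, so that adjustment does not change what is estimated.
4. **Section 7.4, interaction.** Pre-specify one exploratory arm-by-sex interaction on that same scale, with arm effects and confidence intervals for parents of sons and of daughters. Label it as low-powered, and as a test of the combined message, not of the gender wording alone.

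The cost is a few sentences and at most one questionnaire item. The sample size is unchanged. The downside is an imprecise interaction estimate, which the labelling covers.

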## 8 Subject Confidentiality

Confidentiality throughout the trial is maintained by keeping informed consent forms and questionnaires in separate locations, and destroying the questionnaires after they have been input into an electronic database. Informed consent forms will be kept for a period of time designated by the IRBs. The informed consent forms and questionnaires will be in a locked locker, in a locked room, at the Shanghai CDC, which is a complex of buildings with guards at each entrance.

The data will initially be stored in a secure online platform – such as Box – which is HIPAA compliant and which the University of Michigan supports. While the data are being collected, and while some personally identifiable information may be present in the database, this folder will be password-locked and only available to study team members.

We will also keep a record linking the participants' ID number to their vaccination record number. This linkage file will be kept separate from the questionnaires, and it will be on the hard drive of a computer at the Shanghai CDC. The computer will be password-locked and will only be accessible to study team members.

### 8.1 Future Use of Stored Specimens

This study does not include any biological specimens.

Although participant information will be de-identified from the main dataset, a separate linkage file will show their name, their study ID, their vaccination record ID, and their contact information. We will use this information to contact them in the future and to obtain their vaccination records.

## 9 Informed Consent Process

Many parents and children visit vaccination clinics every day in China to receive mandatory vaccines. They wait in line until they are called to visit with a nurse (“vaccination provider”), who discusses vaccination options with them, and then directs them to another nurse who will obtain the vaccines they need and administer the dose(s) required. Afterward, the parents and children are supposed to wait at clinics for 30 minutes after vaccination to see if there is any adverse reaction to the vaccine. A large age range of children come into the clinic, and so we will notify the vaccination providers what are required age range is (2-18 years), and parents of those children will then be told by the nurses about our study. The nurses will mention to parents whose children fall into the age category (2-18 years) that a study is taking place about their attitudes towards vaccination. Vaccination providers will then direct parents to come into a private room to learn more about the study. Of course, some parents may be uninterested at this point and we would never see them. At the end of our time at each clinic, we will ask the nurses how many parents did not come and see us (so we can tally up our response rate).

Clinics have a few private rooms for conducting meetings which are out of the way from where other parents are waiting (before and after vaccinations). Within such a room we will ask parents the screening question (is their child between 2-18 years), and if they answer affirmatively, give the parents the informed consent form and ask if they want to voluntarily participate in this study. We will give them time to read through the document and sign and ask any questions to study staff.

Similarly, for parents sampled at schools, the forms (questionnaire, enrollment log, and informed consent form) will be sent by the teacher to the child’s home. The teacher will be responsible for collecting these documents and handing them back to the study team.

If they sign the informed consent, we will file it in a separate location from the questionnaires. This questionnaire is something that the parents can fill out themselves, and study staff will be available to answer any questions.

Any follow-up survey (i.e., 3 years later) will involve the parents being re-consented.

### **Supplements and Appendices**

None
